### **Randomization:**

[figure not shown]
After obtaining an informed consent, study staff will complete a baseline assessment consisting of measures of cognition, physical function, depression and anxiety, and quality of life (see measures section 4.3.l. below). Blood samples will also be collected from the participants at the time of baseline assessment. Baseline may be completed at subject's home after hospital discharge if unable to complete full assessment in the hospital. After initial assessment, study subjects will be randomized to study groups. Randomization will be stratified by discharge location (home, other facility) and managed by the IU site

[During COVID-19 health crisis, baseline assessments will be completed via phone; abbreviated measures of cognition, and no measures of physical function will be obtained due to the limitations of phone administration. Blood samples will not be collected.]

## 5. Study Procedures

Enrolled subjects randomized to the experimental intervention will receive cognitive training via computer-accessed online training modules 45 minutes per session, 2 days per week for 3 months; and physical exercise delivered by trained facilitators to participants in their homes via internet-based single or multi-party (2-6 per group) videoconference 45 minutes per session, 3 times per week for 3 months (Figure 3).

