Our team is proposing a 2x2 factorial design randomized controlled trial (RCT) called "Decreasing Alzheimer's Disease and Related Dementias after Delirium-Exercise and Cognitive Training (DDD-ECT)" to evaluate the efficacy of 12 weeks of combined physical exercise and cognitive training on the primary outcome of cognitive function among older ICU survivors who experienced delirium or subsyndromal delirium during their ICU stay. We propose to deliver these interventions via a facilitator-led, small group format using internet-enabled, multiparty-videoconference delivered directly into the participants' homes to achieve the following aims:

**Primary Specific Aim: Determine the effect of the combined physical exercise and cognitive training on the cognitive function of ICU survivors aged 50 and older.** Hypothesis: In comparison to older ICU survivors randomized to attention control or either intervention alone, those randomized to 12 weeks of combined physical exercise and cognitive training will have higher total index cognitive scores as assessed by the Repeatable Battery for the Assessment of Neuropsychological Status (RBANS) at 3 and 6 months post randomization.

**Secondary Specific Aim 1: Determine the effect of the combined physical exercise and cognitive training on physical performance, anxiety and depressive symptoms, and quality of life of ICU survivors aged 65 and older.** Hypotheses: In comparison to older ICU survivors randomized to attention control or either intervention alone, those randomized to 12 weeks of combined physical exercise and cognitive training will have higher physical performance as measured by short physical performance battery (SPPB) and two-minute step test, lower mood and anxiety symptoms as measured by Patient Health Questionnaire (PHQ-9) and Generalized Anxiety Disorder (GAD-7) scale, and higher quality of life as measured by the Medical Outcomes Study 36-item short form (SF-36) at 3 and 6-months post randomization.

**Exploratory Aim 1: To examine the mechanisms of action of combined training.** Hypothesis: At the completion of treatment, the combined intervention group will show reduced serum levels of CRP, IL-1, IL-6, IL-8, TNF- $\alpha$ , S-100 $\beta$ , and GFAP and increased levels of BDNF, VEGF, and IGF-1 compared to the attention control, or either intervention alone groups.

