point exertion scale. Participants will also be given Velcro weight bands specific for the wrists and ankles that are color-coded by weight to allow the Interventionist to check that the appropriate weight is used by each participant during video-conference sessions. The initial wrist weights will be 1 pound and the ankle weights will be 2 pounds, although the participants will have the option of 1-pound weight or no weight. Although small group (e.g., 2 to 6) format is the goal, we will start with one-on-one training with escalation into a group. We will continue one-on-one in cases of difficult adherence or unique physical abilities.

**Physical Exercise Control:** This consists of up to 10 minutes of gentle stretching. We will deliver 3 sessions per week for 3 months. This stretching module was designed specifically as a control condition for exercise trials and was used as such in the NIH-funded LIFE exercise trial. Heart rate, oxygen saturation and RPE will be collected as in the Exercise Intervention.

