**Intervention Delivery - Computer and Videoconference in the Home:** This feature is common to all treatment arms. Study staff will initiate contact within 2 weeks post-ICU discharge to set up the computer and videoconference system in subjects' homes. Afterwards, the interaction between the interventionists and the subjects will happen remotely through a computer video interface. Communication via videoconference can be described as live, interactive television. The participants can hear and see one another and the interventionist; and the interventionist can hear and see the participants. We will use New Inspiron One 20" All-in-One Desktop Dell computers, which have the processor and webcam built-in to the 20" monitor. Internet access will be provided with 4G LTE air cards or jet packs will use Zoom for video conferencing provided by Indiana University. The videoconferences will be security protected with room access provided on an individual level. Information technology support, including computer and software settings, will be reviewed and addressed remotely as needed during sessions using TeamViewer software. We have installation, training, and IT support manuals in place. At the initial installation, our staff will orient the subject and family caregiver to the operational features of the computer and Internet interface. Additional orientation visits can be scheduled at the request of the participant or if the Interventionist detects difficulties in a subject's ability to operate the computer. In addition, we have the capability to run the interventions with smaller groups or even single participant groups as needed.

**[During COVID-19 health crisis, computers will be delivered to subject's homes following a no-contact drop-off protocol. Interventionists will provide instructions via phone on how to set up the computer. As long as in-person research activities are restricted, "additional orientation visits" will not be conducted.]**

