## 8. Statistical Considerations

To verify the comparability of the randomized groups, patients' baseline characteristics among the four groups will be compared using analysis of covariance (ANCOVA) for continuous variables and the Cochran-Mantel-Hansel statistic for categorical variables while adjusting for age group. We will examine the distributions of continuous variables and use alternative approaches such as transformation or nonparametric methods in cases of violation to the normal distribution assumption. We will also examine the frequency distribution of all categorical variables and adopt exact inference procedures in cases of zero or small cell size. All analyses will be conducted using the SAS 9.4 (SAS Institute, Carey, North Carolina).

**Primary Specific Aim:** Mixed effects models will be used with repeated RBANS scores collected at baseline, 3 months and 6 months as the outcome measures, group, time and a group by time interaction as independent variables while adjusting for stratification variables and other potential baseline covariates found to be significantly different in univariate comparisons. A significant interaction between group and time would indicate differences in changes of cognitive functions over time among the four groups. Post-hoc comparisons will be conducted following a significant interaction between group and time to compare the effect of the combined training group to the other three groups (attention control, cognitive training only, and exercise only groups) at 3 month for immediate training effect and at 6 month for sustained training effect. Separate mixed effect models will also be used for repeated, Trail Making A&B, and Stroop Color and Word Test scores.

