Sample Size and Power: Cognitive training had been found to have a moderate effect size of approximately 0.5 SD and the combined training was found to have a larger effect size of 0.9 SD when comparing to the control group in healthy elderly subjects. Assuming effect sizes of 0.4 SD in the cognitive training only group and the exercise only groups at 3 and 6 month post baseline compared to the attention control group and effect size of 0.8 SD in the combined training group at 3 and 6 month post baseline compared to the attention group, a sample size of 60 patients in each group will yield 83% power at detecting a significant group by time interaction in a mixed effect model adjusting for correlations of 0.2 for outcomes measured 3 month apart and correlations of 0.1 for outcomes measured 6 month apart at  $\alpha=0.05$ . The power estimation was conducted using the GLMPower procedure in SAS. To further assume that 30% patients may miss some post-baseline assessments, we will need to enroll a total of 344 patients into the study (86 patients per group). Outcomes in Secondary Aim 1 will also have 83% power to detect effect sizes similar to those described for the Primary Aim. For Secondary Aim 2, we will have 81.7% power to detect an overall treatment effect in changes in biomarkers with effect sizes of 0.31 SD in the cognitive training only and the exercise only groups and 0.62 SD in the combined training groups at  $\alpha=0.05$  using one-way ANOVA and the Power procedure in SAS.

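### Exercise is meant to run in small facilitator-led groups, but the primary model and the 83% power treat patients as independent; the likely effect is modest and a sensitivity analysis would cover it

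*Combined protocol and SAP*

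**What the plan says.** **Delivery.** The aims in section 2 state: "We propose to deliver these interventions via a facilitator-led, small group format". Section 5 gives the exercise format as "internet-based single or multi-party (2-6 per group) videoconference", three 45-minute sessions a week for 3 months. Under Physical Exercise Intervention it adds: "Although small group (e.g., 2 to 6) format is the goal, we will start with one-on-one training with escalation into a group", and then: "We will continue one-on-one in cases of difficult adherence or unique physical abilities". Under Intervention Delivery it says of the home videoconference system: "This feature is common to all treatment arms". The Physical Exercise Control paragraph does not say whether stretching is run in groups. Cognitive training is online work at the patient's own computer.

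**Analysis.** The primary model for repeated RBANS scores (section 8, Primary Specific Aim) has "group, time and a group by time interaction as independent variables while adjusting for stratification variables", plus baseline covariates found to differ. Group there means the randomized arm. No training-group or facilitator term appears, and the secondary models have the same structure.

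**Power.** Section 8 states that "a sample size of 60 patients in each group will yield 83% power" for the group-by-time interaction. The only correlations used are within a patient over time: 0.2 at 3 months apart and 0.1 at 6 months apart. The documents mention no ICC or design effect.

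**The concern.** Patients who train together share a facilitator and peers, so their later outcomes may be more alike than those of other patients in the same arm. Individual randomization prevents allocation bias but not correlation that arises afterwards from shared delivery. If that correlation is positive and the model ignores it, standard errors for arm differences in change are too small, confidence intervals too narrow, and the true error rate above the nominal 5%. Power calculated for independent patients is then too high. The contrast of combined training with exercise alone is the most exposed, because exercise may be grouped in both of those arms.

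**Working it through.** **Inputs from section 8.** 60 evaluable patients per arm; SD 1; effects against control of 0.4 SD (each single arm) and 0.8 SD (combined) at both 3 and 6 months; correlations 0.2 and 0.1; alpha 0.05.

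**Step 1: reproduce 83%.** Change from baseline has variance 2(1 − 0.2) = 1.6 at 3 months and 2(1 − 0.1) = 1.8 at 6 months. The covariance of the two changes is 1 − 0.2 − 0.1 + 0.2 = 0.9. The information on an effect that is equal at both visits is s = (1.6 + 1.8 − 2×0.9)/(1.6×1.8 − 0.9²) = 1.6/2.07 = 0.773 per patient. Arm mean changes are 0, 0.4, 0.4 and 0.8, and deviate from their mean by −0.4, 0, 0 and 0.4. The noncentrality is 60 × (0.16 + 0.16) × 0.773 = 14.84. A noncentral F with 6 and 468 degrees of freedom (Hotelling-Lawley) gives 83.3%. Other multivariate statistics move this, and the figures below, by about a point. Enrolment also reproduces: 60/0.7 = 85.7, so 86 per arm and 344 in total. The 83% therefore contains no allowance for clustering.

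**Step 2: add clustering.** Baseline is measured before randomization (section 4), so training together can affect only the 3- and 6-month scores. For groups of size m, let a = (m − 1) × ICC. A grouped arm's information falls from s to s/(1 + a·s). Example, all four arms, m = 6, ICC 0.05: a = 0.25, information 0.773/1.193 = 0.648, noncentrality 60 × 0.32 × 0.648 = 12.44, power 74.9%.

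Assumed: the ICC, m, and every patient in a grouped arm belonging to one stable group.

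| ICC | m | a | Power, two exercise arms grouped | Power, four arms grouped |
|---|---|---|---|---|
| 0.01 | 4 | 0.03 | 82.8% | 82.2% |
| 0.02 | 4 | 0.06 | 82.3% | 81.2% |
| 0.05 | 4 | 0.15 | 80.8% | 78.2% |
| 0.05 | 6 | 0.25 | 79.2% | 74.9% |

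**Step 3: error of pairwise comparisons of change.** With v = 1.6 or 1.8, the true variance exceeds the modelled one by a factor 1 + a/v if both compared arms are grouped, or 1 + a/(2v) if one is. The error rate is 2(1 − Φ(1.96/√factor)).

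| ICC | m | One arm grouped | Both arms grouped |
|---|---|---|---|
| 0.02 | 4 | 5.2% | 5.4% |
| 0.05 | 4 | 5.5% | 6.0–6.1% |
| 0.05 | 6 | 5.8–5.9% | 6.6–6.8% |

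For the overall interaction test, simulation (20,000 replicates) at ICC 0.05 with groups of 4 and 6 gave 5.8% and 6.0% with two arms grouped, and 6.7% and 8.0% with four.

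**Step 4: which random effect helps.** A group intercept that is constant over time cancels from change from baseline, as a patient intercept does. In simulation with groups of 6 and ICC 0.10, adding one left the interaction standard error unchanged and rejection at 8%. A group effect acting only after baseline widened the standard error by about 15% and restored 5%. Arithmetic agrees: a = 0.5, and √(1 + 0.5/1.6) = 1.146.

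**The case against.** The best defence is that the format is looser than fixed cohorts. Sessions may be single, everyone starts one-on-one, some patients stay so, and section 5 (Potential Problems and Alternative Strategies) offers varied times, make-up sessions and individual sessions. All of this weakens clustering by training group, so the Step 2 and Step 3 figures are upper estimates for that source at the stated ICCs. The ICC may also be negligible: at 0.01 with groups of 4 the loss is about one point or less. Both points stand. They limit the size but do not remove the omission, and without recorded IDs the correlation cannot be estimated later.

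A reader might go further and apply the usual design effect, 1 + (m − 1) × ICC, to every arm and visit. At ICC 0.05 with groups of 4 and 6 that gives power of 76% and 72%, and pairwise errors of 6.8% and 8.0%. The documents do not support this. Baseline precedes the training, the planned contrast is change from baseline, and grouping is documented only for exercise. If only exercise is grouped, two of the three planned comparisons (with control and with cognitive training alone) have just one grouped arm.

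A reader might also infer that facilitator clustering is the larger problem, since a facilitator may see more patients than one group holds and one-on-one delivery does not remove it. That is possible, but the documents state neither how many facilitators there are nor whether they work across arms, so it cannot be sized.

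**Conclusion.** The omission is real and its likely effect modest. For any positive within-group correlation, the 83% is too high and the planned standard errors are too small. For ICCs of 0.02 to 0.05 and groups of 4 to 6, taken over the cases tabulated, the power loss is about 1 to 4 points if only the two exercise arms are grouped, and about 2 to 8 points if all four are. Pairwise error stays below 7%.

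These figures rest on an assumed ICC, stable groups, full participation in groups and a shared effect after baseline only. Whether stretching is grouped decides which power column applies. Nothing here shows that the primary analysis is invalid or that the sample size must change. This is a cheap improvement to the analysis and to the power statement.

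**What to change.** 1. Add a training-group ID and an interventionist ID to the session attendance data that trainers already record (section 6, Sources of Materials).
2. Prespecify one partially nested sensitivity version of the primary model. Its training-group random effect acts only on the 3- and 6-month outcomes and is zero at baseline, with one-on-one patients as singletons. Do not use a time-constant group intercept (Step 4).
3. Always report its intervals beside the primary ones. Making this depend on whether the group variance looks negligible would leave reporting to the data.
4. Add an interventionist effect in the same way only if there are enough interventionists to estimate it.
5. State in section 8 that 83% assumes no within-group correlation, and give the power range above with its assumptions.

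Cost: two ID fields and one more model run. The downsides are slightly wider sensitivity intervals, a less favourable power statement, and a group ID that is only approximate where membership changes. The primary model, sample size and delivery of the interventions stay as they are.

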**Cognitive Intervention:**  
The cognitive portion of the combined intervention consists of a suite of 24 programs called Brain HQ developed by Posit Science, Inc. The modules are designed to improve time-order judgment, visual discrimination, spatial-match, forward-span, instruction-following, and memory. The program systematically reduces stimulus presentation time to maintain an 85% accuracy rate and launches each new session based on the stopping point of the preceding session.

**Cognitive Control:** This consists of up to 20 minutes of puzzles and games, 2 days per week for 3 months. We will use on-line Brain HQ Control Games developed by Posit Science, Inc.

**Physical Exercise Intervention:** The physical exercise portion of the combined intervention consists of 45 minutes of multi-modal physical exercise focused on seated aerobic and progressive resistance training designed to improve aerobic capacity, muscular strength and endurance consistent with current exercise recommendations. We will deliver 3 sessions per week for 3 months. Each physical exercise session will be divided as follows: 5 minutes of warm-up, 10 minutes of upper-body, 10 minutes of core, 10 minutes lower-body, 5 minutes of upper-body and lower-body, and 5 minutes of cool-down and flexibility exercises. All exercises are conducted from a seated position in a solid backed chair. We will provide participants with a heart rate monitor watch or pulse oximeter and have participants report their heart rate and oxygen saturation. Their heart rate should be above 55% but not to exceed 70% of their age-adjusted maximum heart rate thus providing moderate-intensity exercise for each participant. Due to limited heart rate response for participants on beta-blocker medications, we will also use the Rating of Perceived Exertion scale (RPE). Participants will be advised to exercise at the RPE level of 5 to 6 on a 10-point scale. Generally, for adults over the age of 40 years, moderate-intensity is 5 to 6 on a 10-

point exertion scale. Participants will also be given Velcro weight bands specific for the wrists and ankles that are color-coded by weight to allow the Interventionist to check that the appropriate weight is used by each participant during video-conference sessions. The initial wrist weights will be 1 pound and the ankle weights will be 2 pounds, although the participants will have the option of 1-pound weight or no weight. Although small group (e.g., 2 to 6) format is the goal, we will start with one-on-one training with escalation into a group. We will continue one-on-one in cases of difficult adherence or unique physical abilities.

**Physical Exercise Control:** This consists of up to 10 minutes of gentle stretching. We will deliver 3 sessions per week for 3 months. This stretching module was designed specifically as a control condition for exercise trials and was used as such in the NIH-funded LIFE exercise trial. Heart rate, oxygen saturation and RPE will be collected as in the Exercise Intervention.

**Intervention Delivery - Computer and Videoconference in the Home:** This feature is common to all treatment arms. Study staff will initiate contact within 2 weeks post-ICU discharge to set up the computer and videoconference system in subjects' homes. Afterwards, the interaction between the interventionists and the subjects will happen remotely through a computer video interface. Communication via videoconference can be described as live, interactive television. The participants can hear and see one another and the interventionist; and the interventionist can hear and see the participants. We will use New Inspiron One 20" All-in-One Desktop Dell computers, which have the processor and webcam built-in to the 20" monitor. Internet access will be provided with 4G LTE air cards or jet packs will use Zoom for video conferencing provided by Indiana University. The videoconferences will be security protected with room access provided on an individual level. Information technology support, including computer and software settings, will be reviewed and addressed remotely as needed during sessions using TeamViewer software. We have installation, training, and IT support manuals in place. At the initial installation, our staff will orient the subject and family caregiver to the operational features of the computer and Internet interface. Additional orientation visits can be scheduled at the request of the participant or if the Interventionist detects difficulties in a subject's ability to operate the computer. In addition, we have the capability to run the interventions with smaller groups or even single participant groups as needed.

**[During COVID-19 health crisis, computers will be delivered to subject's homes following a no-contact drop-off protocol. Interventionists will provide instructions via phone on how to set up the computer. As long as in-person research activities are restricted, "additional orientation visits" will not be conducted.]**

**Safety:** We have incorporated exercise program elements that are associated with lower risks of cardiovascular complications and muscular injury. These include warming up, flexibility exercise, moderate intensity exercise, and a gradual progression of exercise intensity and duration. The Interventionist will educate subjects about the signs and symptoms of angina, myocardial infarction, and muscle/tendon related injuries and how to respond to them; a procedure recommended by the American College of Sports Medicine and the American Heart Association as effective means of reducing complications to exercise. The frequency, duration, and intensity of intervention delivery will be modified as necessary for enrolled subjects who are medically frail. We have outlined our Data and Safety Monitoring Plan including the identification and response to serious cardiac events and orthopedic injuries in the Protection of Human Subjects section. Cognitive training is relatively safe but anxiety and burden will be monitored. As subjects recover from their ICU hospitalization, they may require additional resources to address a variety of ICU survivorship issues. A list of resources will be

provided to all subjects after enrollment. Subjects who express needs to the study team will be referred to resources on the list. If a participant indicates suicidal ideation on the PHQ-9, the patient's care team will be notified. Suicidal ideation of participants at IU affiliated institutions will also be reported to [name] and [name] (clinical psychiatrist working at IU Center for Aging Research) for additional follow up; suicidal ideation of participants at non-affiliated institutions will be reported to the site PI, [name], and [name].

**Potential Problems and Alternative Strategies:** We have measures in place to ensure retention including availability of make-up sessions and availability of individual training sessions. We will request Cognitive Intervention adherence data from Posit Science. If retention drops below 80%, we will have the study staff follow-up with the study participant to troubleshoot any technical issues and provide coaching. Physical training sessions will be offered throughout the week on varying days and times, including the weekends to provide ample training opportunities and make-up sessions. We will use fair subject payments contingent on the completion of the 3 and 6 months follow-up assessments to maximize participation. Loss of information could occur if subjects are unable to complete outcome assessments. To estimate the treatment effect in key domains, a "step-down" battery, consisting of a subset of outcome measures, will be administered when a participant is not able to tolerate the full outcome assessments. This "step-down" battery may also be administered via phone if subject is unable to complete an in-person assessment for the 3 or 6 month outcomes. We also can provide assistive devices (glasses, headphones or pocket talker) if a participant's visual or auditory acuity declines and interferes with interventions or outcome assessments.

**Outcomes Assessments:** Trained and blinded research assistants will complete 3 and 6 months outcomes assessments consisting of measures of cognition, physical function, depression and anxiety, and quality of life (see Outcome Measures section 9 and Figure 3). Data will be collected using Research Electronic Data Capture (REDCap). We will employ multiple techniques to ensure concealment of outcomes assessment. Our research assistants are trained not to inquire about study assignments. They will be conducting structured assessments that do not provide room for qualitative interviewing that should prevent unblinding. They will not be involved in study assignments and training interventions. Subjects will be instructed not to discuss their training intervention with the research assistants.

The following instruments will be used during outcome assessments: Repeatable Battery for the Assessment of Neuropsychological Status (RBANS), Trail Making Test Part A and B, Stroop Color and Word Test, Short Physical Performance Battery (SPPB), Grip Strength, 2-minutes Step Test, Patient Health Questionnaire-9 (PHQ-9), Generalized Anxiety Disorder Scale (GAD-7), Medical Outcome Study Short Form (SF-36), and the International Physical Activity Questionnaire (modified).

**[During COVID-19 health crisis, outcomes assessments will be completed via phone; abbreviated measures of cognition, and no measures of physical function will be obtained due to the limitations of phone administration. Blood samples will not be collected.]**

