## 9. Outcome Measures

[During COVID-19 health crisis, outcomes assessments will be completed via phone; abbreviated measures of cognition, and no measures of physical function will be obtained due to the limitations of phone administration. Blood samples will not be collected.]

**Cognitive Outcome Measures:** The Repeatable Battery for the Assessment of Neuropsychological Status (RBANS) total index score will provide the primary outcome for the trial. Secondary outcomes will be assessed using individual neuropsychological tests of processing speed, executive control, and new learning ability as follows: Trail Making Test Parts A and B (seconds to complete), and Stroop Color and Word Test (interference trial). These measures sample major domains of cognition affected in ICU survivors.

**Physical Performance and Cardiovascular fitness:** Physical training effects on balance and strength will be assessed via the Short Physical Performance Battery (SPPB), a validated objective assessment. The SPPB yields a performance score of 0-12 (0-4 poor, 5-7 intermediate, 8-12 good). A difference of 1 point indicates a significant change in function. Physical training effects on cardiovascular fitness will be assessed via the 2-minute step test. We have selected the 2-minute step test for cardiovascular fitness because it is a validated measure of aerobic capacity, does not require equipment, and can be used in the home setting. Grip strength with dominant hand will also be measured.

**Self-reported Mood and Anxiety symptoms:** We will use the Patient Health Questionnaire–9 (PHQ-9) and Generalized Anxiety Disorder Scale (GAD-7) to determine the impact of the intervention on ICU's survivors' mood and anxiety. The PHQ-9 is a nine-item depression scale with a total score from 0 to 27 and the GAD-7 is a seven-item anxiety scale with a total score from 0 to 21. Both of these scales are derived from the Patient Health Questionnaire, have good internal consistency, and test-retest reliability as well as convergent, construct, criterion, procedural and factorial validity for the diagnosis of major depression and general anxiety disorder.

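### Weight bands are described only for the two exercise arms, and the listed blinding safeguards do not cover equipment an assessor could see at an in-person 3- or 6-month visit

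*Combined protocol and SAP*

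**What the plan says.** Section 5 issues wrist and ankle weights within the Physical Exercise Intervention: "Participants will also be given Velcro weight bands specific for the wrists and ankles that are color-coded by weight". That component belongs to the exercise-only and combined arms. Use of the weights is flexible, "although the participants will have the option of 1-pound weight or no weight".

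The Physical Exercise Control is described differently: "This consists of up to 10 minutes of gentle stretching". No weights are mentioned there. Monitoring is matched, "Heart rate, oxygen saturation and RPE will be collected as in the Exercise Intervention", and of the computer and videoconference set-up the plan says "This feature is common to all treatment arms".

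For follow-up, Section 5 (Outcomes Assessments) states: "Trained and blinded research assistants will complete 3 and 6 months outcomes assessments". The concealment measures it describes are these: "Our research assistants are trained not to inquire about study assignments"; the assessments are structured; assessors take no part in assignment or training; and participants are told not to talk about their training. Section 5 (Potential Problems and Alternative Strategies) treats in-person assessment as the norm and a shortened telephone battery as the fallback. During the COVID-19 period all outcomes are collected by telephone.

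The place of the in-person 3- and 6-month visits is not given. Section 9 chose the 2-minute step test partly because it "does not require equipment, and can be used in the home setting".

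**The concern.** On the text, the bands are the one physical item that separates exercise from non-exercise participants. Training runs for 3 months at three sessions a week, and Section 9 (Collection of Biological samples) describes the 3-month point as immediately after training. The bands would thus be in recent use when the 3-month assessor arrives. None of the described safeguards addresses what the assessor can see, and nothing says that the bands are collected or put away first.

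RBANS (the primary outcome), SPPB and the step test are performance tests run by the assessor. An assessor who knows that a participant exercised could encourage or score differently without intending to. That would favour the combined arm over cognitive-only and over attention control, which are two of the three comparisons that Section 8 plans for the combined arm. Section 8 contains no check on whether blinding held.

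**Working it through.** **Can the bands be seen, and what would they show?**

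1. Where visits take place. Home is explicit only for baseline (Section 4, Randomization; Section 6, Sources of Materials), before randomization. For follow-up it is an inference from three places: the step test's suitability for the home (Section 9); the fall-risk text, which cites about 2,000 in-home assessments in another study and says the same training and supervision procedures will be used here (Section 6, Protections Against Risk, item 2); and the text on the 3-month blood sample, which cites home collection in other projects (item 5).
2. What the bands show. They show exercise versus no exercise. Four arms narrow to two. Cognitive training leaves no such trace, because the computer is common to all.
3. Which comparisons are exposed. Combined versus cognitive-only and combined versus attention control are. Combined versus exercise-only is not, since both arms have bands.

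**The plan's own figure first (Section 8, Sample Size and Power)**

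Inputs: 60 per group; SD 1; correlations 0.2 (3 months apart) and 0.1 (6 months apart); effects at 3 and 6 months of 0, 0.4, 0.4 and 0.8 SD; α = 0.05.

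- Variance of the 3-month change: 2(1 − 0.2) = 1.6. Variance of the 6-month change: 2(1 − 0.1) = 1.8. Covariance: 1 − 0.2 − 0.1 + 0.2 = 0.9.
- With the same shift at both visits, the information per participant is (1.6 + 1.8 − 2 × 0.9)/(1.6 × 1.8 − 0.9²) = 1.6/2.07 = 0.773.
- Noncentrality = n × 0.773 × Σ(δ_g − mean δ)² = 60 × 0.773 × 0.32 = 14.84.
- The Hotelling-Lawley F approximation (6 numerator df) gives 82.9% power. The plan states 83%, so the figure is reproduced.
- Enrollment: 60/0.7 = 85.7, rounded up to 86 per group; 4 × 86 = 344, as stated.

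**The same model with no treatment effect and an assumed assessor bias b in both exercise arms at both visits**

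The shifts are 0, 0, b, b, so Σ(δ_g − mean δ)² = 4 × (b/2)² = b².

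| b (assumed) | Noncentrality, 60 × 0.773 × b² | False interaction |
|---|---|---|
| 0 | 0 | 5% |
| 0.1 SD | 0.46 | about 7% |
| 0.2 SD | 1.86 | about 14% |

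**Combined versus cognitive-only at one visit, without the interaction gate (60 per arm)**

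z = b/√(2/60) = b/0.1826, and rejection = Φ(z − 1.96) + Φ(−z − 1.96).

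- b = 0.1: z = 0.548; 7.9% + 0.6% = 8.5%.
- b = 0.2: z = 1.095; 19.4% + 0.1% = 19.5%.

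These count rejection in either direction. False benefit alone goes from 2.5% to 7.9% and 19.4%.

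**With the gate that Section 8 specifies (pairwise tests only after a significant interaction)**

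Simulating the procedure, with the pairwise test on change from baseline to 3 months, gives a false benefit of combined over cognitive-only in about 2% of trials at 0.1 SD and 5% at 0.2 SD, against 0.6% with no bias.

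**Scale**

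Biases of 0.1 and 0.2 SD are 25% and 50% of the 0.4 SD assumed for a single component.

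**The case against.** The strongest reply is that this is a possibility and not a demonstrated failure, and much of that reply stands. A reader might infer more than the documents support in five ways.

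- That assessors are known to test at home. No section says so for 3 or 6 months.
- That the bands give away the arm. They reveal only the exercise factor. Nor does the bias simply favour the arms expected to do best, because Section 8 assumes the same 0.4 SD for cognitive-only as for exercise-only.
- That the two exercise arms pooled against the other two (120 versus 120) show the damage. At 0.1 and 0.2 SD that test would reject in 12.1% and 34.1%, but Section 8 plans no such contrast.
- That the 8.5% to 19.5% range is the trial's false-positive rate. It ignores the interaction gate and counts both directions.
- That every exercise participant is exposed. Participants may use no weight, telephone visits show nothing, and the 6-month visit falls about three months after training ends. If half the visits were affected, the average bias would halve to 0.05 to 0.1 SD and the ungated figures would fall to 5.9% to 8.5%.

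The existing safeguards also deserve credit: structured testing and the separation of assessors from training limit scoring bias. Putting equipment away may already be done in practice; silence in the protocol does not prove otherwise.

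What remains is that the plan relies on blinded assessors, describes an item that marks the exercise arms, and states no measure against seeing it.

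**Conclusion.** The concern holds as a possible, partial and unaddressed route to unblinding. It rests on two readings of the text: that the stretching control's silence about weights means none are issued, and that in-person follow-up visits are mostly at home. It does not show that blinding has failed.

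The documents give no figure for assessor bias, so its size is illustrative. The bias of 0.1 to 0.2 SD has to be the average over all participants in both exercise arms, which makes the 7% to 14% false-interaction range an upper illustration. The calculation also assumes 60 evaluable participants per arm and the correlations in Section 8. Under the gated procedure, a false finding of combined over cognitive-only stays near 2% to 5%. The effect on the trial's conclusions is likely to be modest, but the remedy costs so little that the sponsor should adopt it.

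**What to change.** Add to Section 5 (Outcomes Assessments):

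1. State where the in-person 3- and 6-month assessments take place.
2. When these visits are booked, staff other than the assessor ask every participant, in all arms, to put all study equipment out of sight before the assessor arrives. Asking all arms alike keeps the request itself from signalling allocation.
3. On the visit form, assessors record whether they saw study equipment or were told the allocation. This is recorded as fact, separately from any guess, and reported by arm.

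Keep every visit in the intention-to-treat primary analysis. Do not exclude visits because the assessor guessed the arm: a guess made after RBANS may follow from the score, and sightings of bands arise only in the exercise arms, so exclusion would be arm-dependent selection after randomization.

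Cost: one line in the booking script and one form item, with no extra staff or visits.
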